Efficacy Study of the LARA Wheelchair System for Subacute Stroke Patients

NCT 02830893

Standard Operating Procedures

February 28, 2018

Table of Content

- 1. Background and Population
- 2. Inclusion and Exclusion Criteria
- 3. Methods
- 4. Timeline of the Study
- 5. Table of Clinical Testing
- 6. List of Clinical Tests
- 7. Daily Study Procedures
- 8. Statistical Considerations

Background

We will recruit 44 individuals with an acute or subacute stroke (3 days to 30 days post stroke) to participate in this randomized controlled trial at UCI ARU and Rancho Los Amigos National Rehabilitation Center. These individuals will have an acute or subacute stroke with arm/ hand weakness defined as a score of less than 50 (out of 66) on the arm motor scale of the Fugl-Meyer Assessment.

Inclusion Criteria:

- 1. History of stroke affecting the arm, at least 3 days to 30 days prior to enrollment
- 2. Age 18 to 80 years of age
- 3. Upper extremity weakness, defined as a score of less than 50 (out of 66) on the arm motor scale of the Fugl-Meyer Assessment

Exclusion Criteria:

- 1. Moderate to severe pain in the stroke-affected upper extremity (score >6 on 10-point visual analog pain scale), at rest or increased when attempting to use LARA
- 2. Severe tone at the affected upper extremity (score >4 on the Ashworth Spasticity Scale)
- 3. Severe aphasia (score of 2 or higher on the NIH stroke scale question 9)
- 4. Deficits in vision, language, attention, or other cognitive functions severe enough to interfere with using LARA
- 5. Currently pregnant
- 6. Difficulty in understanding or complying with instructions given by the experimenter
- 7. Inability to perform the experimental task that will be studied

Methods:

The primary outcome measure will be the Upper Extremity Fugl-Meyer Score to assess motor impairment in the affected arm. Secondary outcome measures will be Box and Blocks Test, Modified Ashworth Scale of Spasticity to measure spasticity of the shoulder, elbow, wrist and hand, Visual Analog Pain scale to assess pain, NIH Stroke Scale, mini mental state exam to assess cognitive function and the Borg scale to access their perceived exertion levels. We will perform testing at three separate evaluations: At the initial baseline visit, 3-weeks post therapy or the day before discharge if sooner, and 3-month follow up. The end point of the study will be the 3-month after baseline evaluation.

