Answers in **bold** and underlined indicate depression. Although differing sensitivities and specificities have been obtained across studies, for clinical purposes a score > 5 points is suggestive of depression and should warrant a follow-up interview. Scores > 10 are almost always depression.

Subject ID:	
Date:	
Exam#:	

Power Grasp Test

	Trial 1	Trial 2	Trial 3	Average
Grasp (kg) Right				
Grasp (kg) Left				

Grasp

- Displays grip force in pounds (0-200) and kilograms (0-90).
- Isometric; accommodates variable size hands, adjusts to five grip positions (1 ¾" to 3 ¾").
- Set adjustable handle to the desired spacing.
- Rotate the peak hold needle counter-clockwise to 0.
- The patient should be seated with shoulder adducted and neutrally rotated, elbow flexed at 90 degrees, and the forearm in neutral position and wrist between 0-30 degrees dorsiflexion and 0-15 degrees ulnar deviation.
- Let the patient comfortably arrange the instrument in hand. Lightly hold around the readout dial to prevent inadvertent dropping
- Have the patient squeeze with maximum strength.
- 3 trials with 2-3 min. rest period between trials.
- The average of the three trials is recorded.
- Compare the other hand and the normative data. Scores within 2 standard deviations of the mean are considered within normal limits.

Subject ID:	
Date:	
Fxam#:	

Pinch Strength Test

Test	Trial 1	Trial 2	Trial 3	Average
Lateral Pinch (kg)				
Right				
Lateral Pinch (kg)				
Left				

Pinch

- Measures key (Lateral Pinch) strength.
- -Measures in pounds (0-45) or kilograms (0-20).
- -ASHT recommends the following test position: patient should be seated, shoulders adducted and neutrally rotated, elbow flexed at 90 degrees, forearm and wrist in neutral position.
- -Key or lateral pinch: pad of thumb and lateral surface of index finger

Daily Procedures:

- 1. Stroke patients admitted to ARU.
- 2. Screen will be done upon admission (within 1-2 days).
- 3. Baseline evaluation will be performed within 1-3 days after the screening visit. The therapist will see patients in a separate room right outside ARU.
- 4. Randomization occurs after baseline evaluation same day if possible. We will use the web-based formula to randomize patients from both study sites.
- 5. Study participants will be assigned to groups the day after randomization and begin their assigned intervention.

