- 9. If supervising therapists at ARU and research therapist believe LARA participants are skilled enough to drive LARA, participants will begin using LARA to go to therapy appointments and move around ARU by themselves.
- 10. 3 clinical evaluations: baseline, 3-week post therapy or the day before discharge if sooner, 3-month follow up. All clinical evaluations must be completed within 2 days of scheduled dates.
- 11. 3-month follow up is 3 months after baseline evaluation.

Statistical Considerations

Data will be analyzed using modified intention-to-treat analysis. That is, all participants will be included in the analysis if data from the last follow-up assessment is available, regardless of treatment they receive or deviations from protocol. For missing data, we will carry forward the last available value. The effect of treatment on each outcome measure will be assessed using a repeated-measures ANOVA. Follow up analysis will be done using t-tests with Bonferroni corrections, or Wilcoxon rank sum tests if the distributions fail the Lilliefors test for normality. We hypothesize that the participants in the LARA therapy group will have significantly greater reductions in motor impairment measured by FM score than participants in the conventional therapy group. We expect this will be due to the increased dose of therapy LARA provides, and we will include total arm activity (as measured by the wrist-mounted actigraphy) and baseline function as covariates in the analysis. We will compare changes in MAL score, ARAT score, range of motion at the shoulder and elbow, Visual Analog Pain scores, Ashworth Spasticity, and 10 min walk scores using student's t-test or Wilcoxon rank sum tests for non-parametric data. We expect improvements in functional use of the impaired limb (MAL and ARAT) and range of motion but expect no significant differences in pain, spasticity, wheelchair odometer reading, or walking speed. All analyses will be reviewed by our statistical consultant.

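### On the natural reading, the only analysis set defined is restricted to participants with 3-month data, and the carry-forward rule does not say which visits it fills

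*Combined protocol and SAP*

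**What the plan says.** Statistical Considerations states: "Data will be analyzed using modified intention-to-treat analysis". It then defines that set: "all participants will be included in the analysis if data from the last follow-up assessment is available". The same sentence goes on to keep participants whatever treatment they received and whether or not they departed from protocol. The next sentence reads "For missing data, we will carry forward the last available value" and names no visit, outcome or group of participants. On the model: "The effect of treatment on each outcome measure will be assessed using a repeated-measures ANOVA".

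The visits are listed in Daily Procedures: "3 clinical evaluations: baseline, 3-week post therapy or the day before discharge if sooner, 3-month follow up", with "3-month follow up is 3 months after baseline evaluation". The Time Line of the Study attaches the word follow-up only to the third evaluation, and Methods says "The end point of the study will be the 3-month after baseline evaluation". On timing of allocation, Daily Procedures says "Randomization occurs after baseline evaluation same day if possible".

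No analysis of all randomised participants, missing-data assumption or sensitivity analysis is described. The documents do not label this set primary, but it is the only one defined and it covers every outcome, including the primary Fugl-Meyer (FM) score.

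**The concern.** Whether someone has 3-month data is known only after randomisation, so the inclusion rule selects on a post-randomisation event. A comparison of completers is biased if loss is related to recovery and either the rate of loss or that relation differs between arms. It is unbiased if loss is unrelated to recovery or, with no true effect, if rate and mechanism are the same in both arms. Participants know whether they have the wheelchair or the towel-and-table programme, so unequal loss is possible; its direction cannot be predicted from the documents.

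The carry-forward sentence adds a second difficulty. Depending on how it is read, two analysts following the text faithfully could analyse different people with different month-3 values, and the choice could be made after seeing the data.

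**Working it through.** **1. What the two sentences do together**

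- *Last follow-up is the 3-month visit (natural reading).* Anyone without month-3 data is already out. Carry-forward can fill only a missed Evaluation 2, with baseline, or a single missing test. It leaves a month-3 comparison adjusted for baseline FM untouched. Its effect on the full repeated-measures ANOVA was not quantified.
- *Carry-forward is meant to fill month 3.* It then conflicts with the inclusion rule.
- *Last follow-up means each participant's own last assessment.* The inclusion rule then changes meaning.

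In the second and third cases, month 3 is filled from Evaluation 2, which may be timed by discharge, or from baseline if Evaluation 2 was also missed.

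**2. Inputs for an illustration**

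From the documents: 44 participants (Background) and a baseline-function covariate (Statistical Considerations). There is no sample-size calculation to reproduce. Assumed: 22 per arm, no true effect, baseline FM with SD 12, early gain 10 (SD 6), later gain 7 (SD 5), and no floor or ceiling. Loss depends on early gain through an odds ratio (OR) per SD. The simulation used 40,000 trials per scenario and compared arms at month 3 adjusted for baseline FM. Actigraphy and the full ANOVA were not simulated.

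SD of total change = sqrt(36 + 25) = 7.81.

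**3. Completers only (natural reading)**

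| Loss pattern | Absolute bias (points) | Type I error |
|---|---|---|
| 19% in both arms, unrelated to gain | 0 | 4.8% |
| 19% in both arms, same OR 2.7 | 0 | 5.1% |
| 19% in both arms, relation in one arm only, OR 1.6 / 2.7 | 0.5 / 1.0 | 5.5% / 6.4% |
| 25% vs 5%, same relation, OR 1.6 / 2.7 | 0.5 / 1.0 | 5.4% / 6.7% |

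Hand check at 19% loss: 22 x 0.81 = 17.8 per arm, so SE = 7.81 x sqrt(2/17.8) = 2.6. A bias of 1.0 is 1.0/2.6 = 0.38 SE, and the two-sided rejection probability is 1 − Φ(1.96 − 0.38) + Φ(−1.96 − 0.38), or about 6.7%. A bias of 0.5 gives about 5.4%.

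These figures are not a ceiling. Suppose the LARA participants lost are exactly those lowest on a variable correlated 0.3 or 0.6 with outcome, and control losses are random. At 20% loss per arm the bias is then 0.10 or 0.21 SD (type I error about 6% or 9.5%). At 30% versus 10% with correlation 0.6 it is 0.30 SD (about 14%).

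**4. Carry-forward to month 3 (alternative readings only), missingness unrelated to gain**

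Bias = difference in missing proportion x (7 x share with Evaluation 2 + 17 x share with baseline only), where 17 = 10 + 7.

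| Value carried | 25% vs 15% missing | 25% vs 5% missing |
|---|---|---|
| Week 3 for all | 0.10 x 7 = 0.7; 5.9% | 0.20 x 7 = 1.4; 8.8% |
| Baseline for half | 0.10 x 12 = 1.2; 7.4% | 0.20 x 12 = 2.4; 14.7% |
| Baseline for all | 0.10 x 17 = 1.7; 8.6% | 0.20 x 17 = 3.4; 22.0% |

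A likelihood-based estimate had absolute bias of at most 0.03 in all scenarios, but those scenarios are missing at random by construction.

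**5. Precision**

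At an assumed 20% loss, 44 x 0.8 = 35.2 remain. The difference detectable with 80% power rises from 0.865 SD (6.8 points) to 0.973 SD (7.6 points), or power at 0.865 SD falls from 80% to 70%. Little of that is recoverable. The simulated SE is about 2.38 with complete data, 2.66 for completers and 2.52 for the likelihood model when those lost have Evaluation 2. When they do not, it is about 2.69, no better than completers.

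**The case against.** The best defence is that the harm on the natural reading is small. Biases of 0.5 to 1.0 point sit against a standard error of about 2.6, and the milder cases barely move the error rate. The larger carry-forward figures belong only to the alternative readings. The design also works against loss: Evaluation 2 is brought forward to the day before discharge when discharge comes early, so few people should have baseline as their last value, and both arms are offered the same $100 per evaluation. The inclusion rule already keeps participants who deviated from protocol. Loss related to recovery only through baseline FM would largely be handled by the planned baseline covariate.

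All of this stands, and it lowers the severity. It does not settle which people are analysed or what carry-forward fills, and it does not protect against loss related to recovery after baseline.

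A reader might infer that this is a per-protocol analysis; the clause on treatment received and deviations rules that out. A reader might also infer type I error of 15% to 22%. That requires values to be carried to month 3, 25% versus 5% missing, and baseline carried for half or all of those missing, and no section suggests this. Nor does any section suggest strong and opposite loss mechanisms in the two arms, which would give 2.0 points and 11.5% for completers.

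**Conclusion.** The concern holds as a matter of definition: on the natural reading, the set called modified intention-to-treat contains only 3-month completers, and the scope of carry-forward is not stated. It should be fixed, but the documents do not show a large bias. The actual size is unknown because dropout, SD and expected gains are absent; every magnitude above rests on assumed values, a 1:1 split and a month-3 comparison simpler than the planned ANOVA. Under the main illustration the bias is zero to about 1.0 point (type I error from 5% to about 7%). If week-3 values are carried to month 3 it reaches about 1.4 points and 9% at 25% versus 5% missing, and more where baseline is carried, which should be uncommon.

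A reader might also infer that a better analysis would restore power from 70% to 80%. It would not: the 80% assumes complete data. The case for change rests on avoiding selection and having one clear rule.

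**What to change.** In Statistical Considerations:

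- Define the main analysis set as all randomised participants, analysed as randomised and still regardless of treatment received or deviations. Baseline precedes randomisation, so baseline FM should exist for all of them.
- Delete the carry-forward sentence.
- Analyse FM at Evaluations 2 and 3 with a likelihood-based repeated-measures model (arm, visit, arm-by-visit, baseline FM), or use multiple imputation within the planned repeated-measures ANOVA. Report the 3-month arm contrast, since month 3 is the stated end point.
- Include participants with no post-baseline FM by multiple imputation, or report their number by arm.
- Keep the completers analysis and one delta-adjusted analysis as sensitivity analyses. The latter shows how far the result depends on missing at random; it does not test that assumption.
- Report missing FM by arm and visit.

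Whether the planned total-arm-activity covariate stays is a separate question that this change does not decide.

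The cost is revised wording and modest extra analysis, with no new data. The downside is reliance on missing at random. In the simulation the likelihood model's standard error was about 2% to 6% smaller than for completers when those lost had Evaluation 2, and no smaller when they did not. Against carry-forward it ranged from about 9% smaller to 14% larger.

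### The Fugl-Meyer test is not tied to the 3-month end point and adjusts for arm activity, the expected mechanism; six other outcomes get change-score tests with no baseline covariate

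*Combined protocol and SAP*

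**What the plan says.** Methods is clear on outcome and time: "The primary outcome measure will be the Upper Extremity Fugl-Meyer Score to assess motor impairment in the affected arm", and "The end point of the study will be the 3-month after baseline evaluation". Testing takes place at baseline, post therapy and 3 months.

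Statistical Considerations then says:

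- **All outcomes.** "The effect of treatment on each outcome measure will be assessed using a repeated-measures ANOVA". No term (group, or group by time) and no visit is named, and it is not stated whether baseline is one of the responses.
- **Fugl-Meyer (FM) hypothesis.** The LARA group is expected to show "significantly greater reductions in motor impairment measured by FM score than participants in the conventional therapy group". The plan attributes this to a larger therapy dose. In the same sentence it adds total arm activity "as measured by the wrist-mounted actigraphy) and baseline function as covariates in the analysis". It does not say that baseline function means baseline FM.
- **Follow-up.** "Follow up analysis will be done using t-tests with Bonferroni corrections, or Wilcoxon rank sum tests", without the contrasts or their number.
- **Six other outcomes.** "We will compare changes in MAL score, ARAT score, range of motion at the shoulder and elbow", together with pain, Ashworth and "10 min walk scores using student's t-test or Wilcoxon rank sum tests for non-parametric data". No visit or covariate is given.

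The Table of Clinical Testing schedules a baseline for FM and for all six.

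**The concern.** Three things follow from these sentences.

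First, the end point and the test are never joined. The primary outcome and its time are stated in Methods, but the result that will count as the FM answer is not identified.

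Second, the treatment contrast is to be adjusted for something the plan itself places between treatment and outcome. If LARA works by increasing arm use, holding arm use equal removes the benefit that the trial is meant to detect.

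Third, the comparisons of change leave available information unused. Baselines are collected for all six outcomes, and a trial of 44 has little precision to spare. For MAL, ARAT and range of motion, where improvement is expected, the loss is in power. For pain, spasticity and walking speed, where no difference is expected, it is a wider confidence interval.

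**Working it through.** **Inputs.** From the documents: 44 participants, two groups, three evaluations. The 44 has no derivation, so there is no planned figure to reproduce. The documents give no SD, effect size, within-patient correlation, allocation ratio or significance level. Assumed: 22 per arm with complete data, equal SDs, two-sided 0.05, an effect of 0.7 SD. The baseline-to-3-month correlation ρ is varied.

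**1. Arm activity.** Let A be arm and M total arm activity, with M = aA + error and FM at 3 months = c′A + bM + error. The total effect of LARA is c′ + ab. Adjusting for M estimates c′ at best, and only if nothing unmeasured drives both M and FM. If the plan's explanation were complete, c′ would be 0 and the adjusted contrast would show nothing even though LARA worked. The documents give neither a nor b, so the shortfall cannot be sized. The actigraphy period is not stated. That it follows randomisation is inferred from the link to therapy dose.

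**2. Change score against baseline adjustment at 3 months** (SD units)

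- Change: SE = √[2(1−ρ) × 2/22], 42 df.
- ANCOVA: SE = √[(1−ρ²)(1 + 1/39) × 2/22], 41 df; the 1/39 allows for chance baseline imbalance.
- Large-sample variance ratio: (1−ρ²)/[2(1−ρ)] = (1+ρ)/2, which is 0.75, 0.85 and 0.95 at ρ = 0.5, 0.7 and 0.9.

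At ρ = 0.5, the change SE is √(1 × 0.0909) = 0.302, so 0.7/0.302 = 2.32 and power is 62%. The ANCOVA SE is √(0.75 × 1.0256 × 0.0909) = 0.264, so 0.7/0.264 = 2.65 and power is 73%.

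| ρ | Power, 0.7 SD: change v ANCOVA | Power, 0.5 SD | 95% CI half-width |
|---|---|---|---|
| 0.5 | 62 v 73% | 37 v 46% | 0.61 v 0.53 |
| 0.7 | 83 v 88% | 55 v 61% | 0.47 v 0.44 |
| 0.9 | >99% both | 95 v 96% | 0.27 v 0.27 |

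**3. The unnamed ANOVA term.** Simulation of a three-visit ANOVA with a constant 0.7 SD effect and Greenhouse-Geisser correction. The correlations (baseline–visit 2, baseline–3 months, visit 2–3 months) are 0.6, 0.5, 0.7 and then 0.8, 0.7, 0.85. Results are for ρ = 0.5 / 0.7.

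| | No baseline covariate | Baseline FM as covariate |
|---|---|---|
| Power, group effect | 42 / 37% | 86 / 96% |
| Power, group by time | 70 / 92% | 81 / 95% |
| The two terms disagree | 51 / 60% of trials | 7 / 2% |
| Type I error if either may be reported | about 9.5% | about 6.7% |

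Under equal correlations between all visits, the covariate model gives 16 / 6% disagreement and about 8% type I error.

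**4. Price of a 3-month contrast.** Power of the 3-month ANCOVA against three-visit group by time without a covariate:

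- Effect fades (0.7 then 0.35 SD): 25 v 60% at ρ 0.5; 35 v 88% at 0.7.
- Effect builds (0.35 then 0.7 SD): 73 v 58%; 88 v 82%.
- Constant effect: 73 v 70%; 88 v 92%. The covariate-adjusted terms in step 3 have more power than the 3-month ANCOVA in this case.

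**The case against.** The best defence is that the plan is less open than it looks. Change wording with three visits points naturally to group by time, and baseline function is already a planned covariate. If that means baseline FM, the choice of term hardly matters (step 3), and naming it is a clarification. Much of this stands.

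A reader might infer from the silence that the two terms would conflict in most trials, or that the false-positive rate would about double. Those figures belong to a three-visit ANOVA with no baseline covariate, which is not the obvious reading of this plan. Group by time with only the two post-baseline visits as responses has 5% power under a constant effect, but it asks whether the effect changes between those visits, which is not the stated hypothesis. It says nothing about how the plan would perform.

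A reader might also infer that the change-score tests are invalid, or that six secondary outcomes are each certainly tested twice. Neither is supported. Change scores subtract baseline and are valid. The change comparisons use the same tests as the Bonferroni follow-up and may simply be that follow-up. The absence of a covariate is read from silence. Of the six, only pain and Ashworth are on the secondary list in Methods.

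It is also fair that a 3-month contrast is not always the most powerful choice. The reason for it is that Methods names 3 months as the end point.

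**Conclusion.** The point holds in a limited form. The missing link between the FM test and the 3-month end point, and the adjustment for the expected mechanism, rest on the text alone. The distortion from the arm-activity covariate cannot be sized, but its direction is clear if the plan's explanation is right: towards understating LARA's effect.

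The precision gain for the six non-primary outcomes is moderate: 11 percentage points of power at ρ 0.5, about 5 at 0.7 and almost none at 0.9, under the assumptions above. Fewer than 22 completers per arm would lower all the powers. This is an improvement that should be made, not an error that invalidates the analysis.

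**What to change.** - **Primary test.** The arm difference in FM at 3 months, adjusted for baseline FM, two-sided 0.05, with a 95% CI. State that baseline function means baseline FM. Treat the ANOVA and the Bonferroni follow-up as supportive.
- **Arm activity.** Leave it out of that contrast and report it only in an exploratory analysis. This changes the plan in substance and should be stated openly.
- **Six other outcomes.** Analyse each once at 3 months, adjusted for its own baseline, with a 95% CI. Use an ordinal model or permutation p-value for Ashworth. Range of motion and Ashworth have several joint scores, so say which score or summary is used.
- **Box and Blocks, NIHSS and MMSE.** Do the same. They are on the secondary list in Methods and have baseline rows in the Table of Clinical Testing. Borg is on the list but has no row, so this does not extend to it.

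The cost is SAP wording and one degree of freedom per covariate, with no new data. The real price is power if the benefit fades before 3 months (25 v 60% at ρ 0.5 in step 4). If the team expects that pattern, it should reconsider the end point openly rather than leave the term unnamed.

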After the baseline evaluation, all participants will be randomized into 2 groups: LARA group versus conventional hand and arm exercise program. Randomization will be done through a web-based program.

For LARA group: participants will be fitted for a LARA chair, they will receive a demonstration by a research therapist and be instructed on how to get in/out of the LARA chair, how to propel LARA in a straight line, turns, figure 8 if possible. Participants will also receive training on how to perform arm exercises using a video gaming program. Participants will receive 2 sessions lasting 30 mins each for these training exercises. Participants will begin his/her exercise routine starting the third session. A research therapist will be available to assist but study participants are expected to perform exercise routines by themselves as much as possible. The research therapist will record and keep a log of time spent assisting study participants every day.

If supervising therapists believe LARA participants are skilled enough to drive LARA, participants will begin using LARA to go to therapy appointments and move around ARU by themselves throughout the study.

For control group: participants will receive a demonstration by a research therapist and instructions on how to perform arm/hand exercise programs using towel and table. Towels, tables and an exercise log will be provided. Participants will receive 2 sessions lasting 30 minutes for each training. Participants will begin his/her exercise routine starting the third session. A research therapist will be available to assist but study participants are expected to perform exercise routines by themselves as much as possible. The research therapist will record and keep a log of time spent assisting study participants every day.

Study participants will be compensated with a cash stipend of \$100 for each evaluation. Study participants will receive a maximum total of \$300 from the study.

Time Line of the Study

Visit	Week	Evaluation	Evaluation	Exercise	Training Content
# 1	1	Session #	content	session #	(order to be randomized)
	1	1	Screen		
2	1	T T	All clinical outcomes		
3	1			1	A: LARA or B: Tabletop exercise program
4	1			2	A: LARA or B: Tabletop exercise program
5	1			3	A: LARA or B: Tabletop exercise program
6	1			4	A: LARA or B: Tabletop exercise program
7	1			5	A: LARA or B: Tabletop exercise program
8	2			6	A: LARA or B: Tabletop exercise program
9	2			7	A: LARA or B: Tabletop exercise program

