10	2			8	A: LARA or B: Tabletop exercise program
11	2			9	A: LARA or B: Tabletop exercise program
12	2			10	A: LARA or B: Tabletop exercise program
13	3			11	A: LARA or B: Tabletop exercise program
14	3			12	A: LARA or B: Tabletop exercise program
15	3			13	A: LARA or B: Tabletop exercise program
16	3			14	A: LARA or B: Tabletop exercise program
17	3			15	A: LARA or B: Tabletop exercise program
18	3	2	All clinical outcomes		
19	13	3	All clinical outcomes: Follow-up		

Table of Clinical Testing

	Screen	Evaluation #1	Evaluation #2	Evaluation #3
		(Baseline)	(Post therapy)	(3-month follow up)
Consent Form	Х			
HIPAA wavier form	Х			
Photography consent	X			
Medical History/ Health Status Questionnaire/ Rehab History overall	Х			
NIHSS	X	X	X	X
Box and Blocks Test		X	X	X
Mini Mental State Exam		X	X	Х
Modified Rankin Scale		X	X	Х
Motor sections of Fugl- Meyer	Х	Х	Х	Х
Action Research Arm Test		Х	Х	Х
Motor Activity Log		X	Х	X
10-meter walk		X	Х	X
Grip Strength		X	X	X
AROM & PROM at shoulder and elbow		Х	Х	Х
Geriatric Depression Scale		Х	Х	Х
Modified Ashworth Scale of Spasticity (Shoulder, Elbow, Wrist, Finger)	Х	Х	Х	Х
Visual Analog of Pain Scale	Х	Х	Х	Х
IMI	Х	X	X	X
Stipend	X	X	X	Х

List of Clinical Tests

- 1. Upper Extremity Fugl-Meyer Motor Score study primary outcome measure
- 2. Box and Blocks Test
- 3. Motor Activity Log
- 4. Action Research Arm Test
- 5. Active and passive range of motion at the shoulder and elbow
- 6. Modified Ashworth Spasticity Scale
- 7. Visual Analog Pain Scale
- 8. 10-meter walk test
- 9. NIH stroke scale
- 10. Mini-Mental State Examination
- 11. Geriatric Depression Scale
- 12. Modified Rankin Scale Score
- 13. Grip Strength

Total Score	/66	
Proximal	/36	Subject ID
Wrist/Hand	[ 24	Date
Coordination/Speed	/ 6	Visit #
Affected side (R or L) _	 	

FUGL-MEYER ARM MOTOR ASSESSMENT Remember to score best, not first, patient performance

Pr	oximal				
LF	Reflexes				
Biceps or finger flexor reflex			0 [no reflex]	2 [reflex elicitable]	
2.	Triceps reflex		0 [no reflex]	2 [reflex elicitable]	
Ш	Flexor Synergy				
		cted to voluntarily bring affect lder abducted 90°/externally	ed forearm fully supinated to rotated/retracted/elevated.	ear of the affected side,	
3.	Shoulder girdle retraction	0 [not done at all]	1 [partly done]	2 [faultless]	
4.	Shoulder girdle elevation	0 [not done at all]	1 [partly done]	2 [faultless]	
5.	Shoulder abduction	0 [not done at all]	1 [partly done]	2 [faultless]	

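### Total arm activity, the plan's own measure of the expected mechanism, is a covariate for Fugl-Meyer, and no test without it is named as decisive

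*Combined protocol and SAP*

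**What the plan says.** The Methods section sets the primary outcome: "The primary outcome measure will be the Upper Extremity Fugl-Meyer Score to assess motor impairment in the affected arm". The List of Clinical Tests repeats it.

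Statistical Considerations assigns the general model: "The effect of treatment on each outcome measure will be assessed using a repeated-measures ANOVA". It then adds: "Follow up analysis will be done using t-tests with Bonferroni corrections", with a rank test as the non-normal alternative. Neither sentence mentions covariates. After stating the FM hypothesis, the section gives the expected mechanism, "We expect this will be due to the increased dose of therapy LARA provides", and in the same sentence the covariates: "we will include total arm activity (as measured by the wrist-mounted actigraphy) and baseline function as covariates in the analysis".

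FM is not among the outcomes listed later in that section for simple change-score comparisons. Actigraphy appears nowhere else: not in the Table of Clinical Testing, the List of Clinical Tests or the Daily Procedures. No recording window is given.

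**The concern.** A covariate in a treatment comparison should be something that treatment cannot change. Baseline function qualifies. Total arm activity probably does not. The plan ties it to the dose LARA delivers and lists it apart from baseline function, and a measure taken before treatment could not reflect that dose. LARA participants also have a possible extra source of arm activity, because they may drive the chair around the unit: "If supervising therapists believe LARA participants are skilled enough to drive LARA".

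A group comparison that holds activity fixed estimates only the part of the LARA effect that does not pass through activity. If the plan's expectation about mechanism is right, that is the smaller part. A real benefit could then be reported as small or absent. Adjusted and unadjusted FM results could also disagree, with no rule for which one counts.

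**Working it through.** **No figure to reproduce.** The plan gives 44 participants in two groups. It gives no significance level, power, effect size, SD, allocation ratio or expected difference in activity. Everything below except the 44 is an assumption made for illustration.

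**Inputs.** 22 per arm (44 / 2, equal allocation assumed); two-sided 5%; total LARA effect 0.866 SD, which gives an exact two-sample t-test 80.1% power at 22 per arm; FM SD of 1 given arm and baseline; LARA raises activity by k SD; a share m of the effect passes through activity.

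**Model.** With group G, baseline FM B and independent noise u and e:
- Activity: M = k·G + 0.6·B + u
- Follow-up FM: Y = c·G + b·(k·G + u) + 0.6·B + e
- Constraints: c + b·k = 0.866, b·k = m × 0.866, and b² + var(e) = 1

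**Estimate.** Substituting k·G + u = M − 0.6·B gives Y = c·G + b·M + (0.6 − 0.6b)·B + e. With M in the model, the group coefficient is therefore c = (1 − m) × 0.866. For m = 0 / 25 / 50 / 75 / 100% this is 0.87 / 0.65 / 0.43 / 0.22 / 0.00 SD, whatever the value of k.

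**Standard error.** Approximately √[(1 − b²)(1 + k²/4)(2/22)]. At k = 1 and m = 50%, b = 0.433, so SE = √(0.8125 × 1.25 × 0.0909) = 0.304 and the ratio is 0.433 / 0.304 = 1.42. Without activity, SE = √0.0909 = 0.302 and the ratio is 0.866 / 0.302 = 2.87.

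**ANCOVA power by simulation** (20,000 replicates, baseline FM in every model; 79% without activity). Power in % with activity, by mediated share:

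| k | 0% | 25% | 50% | 75% | 100% |
|---|---|---|---|---|---|
| 0.25 | 78 | 98 | – | – | – |
| 0.5 | 75 | 60 | 75 | – | – |
| 1 | 69 | 46 | 27 | 13 | 5 |
| 1.5 | 59 | 39 | 21 | 9 | 5 |

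Dashes are impossible combinations, since b must stay below 1: m is at most 0.5 / 0.866 = 58% at k = 0.5 and 0.25 / 0.866 = 29% at k = 0.25. At small k the estimate suffers more than the power. At k = 0.25 and m = 25%, b = 0.866, so activity absorbs 75% of the residual variance. Power rises to 98%, but the estimate still shrinks to 0.65 SD. A separate normal-approximation calculation with a total effect of 0.845 SD gives 71 / 48 / 28 / 13 / 5% at k = 1.

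**Repeated measures.** A group main-effect test on the post-baseline visits follows the same algebra. For the three-visit group-by-time test, the form matters:
- *Activity as a main effect only, complete data:* a covariate that is constant within a participant explains only between-participant variation, so group-by-time does not move. In one simulated data set (k = 1, m = 50%) the two group-by-time estimates were 0.973 and 0.999 (SE 0.267) with or without activity.
- *Activity-by-time added:* in the same data set they fell to 0.695 and 0.678 (SE 0.278). With effect 0.866 at both post-baseline visits, correlation 0.6 between the two changes and k = 1, power is about 85% without activity. With activity-by-time, at m = 50% and 100%, it is about 28% and 6% if baseline-by-time is also in the model, and about 43% and 17% if it is not.

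**The case against.** The strongest reply is that harm needs several links that the plan never states:
- *Timing.* That activity is recorded after randomisation is an inference, though the natural one.
- *Which test.* The covariates are attached to the sentence about mechanism, while the sentence assigning the treatment test names none. The adjusted model may have been meant as explanatory, beside an FM analysis without activity.
- *Model form.* The hypothesis is about reduction in impairment over visits, which suggests group-by-time. Missing values are carried forward, so FM data would be complete for those analysed. Activity as a main effect only would then be harmless.
- *Size of the shift.* Both arms have the same 15 scheduled exercise sessions, and no difference in activity is predicted.

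Each of these is fair, and they limit the claim. A reader might infer that the plan certainly adjusts the LARA effect away, or that it contains no FM test without activity. The documents support neither: an unadjusted ANOVA may be run, and one admissible form does no damage. A reader might also take the statement "expect no significant differences in pain, spasticity, wheelchair odometer reading, or walking speed" as evidence that activity will not differ. It is not, because distance wheeled is not wrist activity.

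What the reply does not supply is a sentence choosing the harmless reading. The phrase about covariates in the analysis most naturally points back to the ANOVA, the t-tests are called follow-up, and activity-by-time is as open as a main effect.

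**Conclusion.** The point holds as a defect of specification in the primary analysis. The plan names a mechanism, enters its measure as a covariate, and neither sets that model apart as exploratory nor says which FM test decides efficacy. Three of the forms it permits remove the mediated part of the effect; one does not.

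Under the assumed inputs with a 1 SD shift in activity, the ANCOVA estimate is halved when half the effect is mediated and vanishes when all of it is. The last case is the plan's own expectation taken literally, if actigraphy captures dose fully. Loss of power is not general: with small shifts in activity the estimate shrinks but power may hold or rise. The three-visit figures also depend on whether baseline-by-time is included. The actual loss in this trial cannot be computed from the documents. Because the primary hypothesis is affected and the remedy is cheap, it should be settled before the data are analysed.

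**What to change.** Name the deciding FM test and keep activity out of it. Suggested wording: 'Efficacy on FM will be decided by the group difference in FM at the 3-month evaluation, adjusted for baseline FM. Total arm activity will not enter this model. Any repeated-measures model of FM will also exclude total arm activity from the test of treatment.'

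This uses the 3-month evaluation that Methods already calls the study end point. It also makes baseline FM a covariate, not one of the outcome visits, so it does not play both parts in the deciding model.

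Where actigraphy is collected, use it in a separately labelled exploratory mediation analysis that states its no-confounding assumptions and does not decide efficacy.

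The cost is wording only: no further participants, visits or measurements.
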